- **Per-protocol Efficacy Analysis Set (PPAS):** The PPAS includes all participants in the PEAS who do not have any protocol deviations that are deemed to potentially impact efficacy.

Assignment of participants to populations will be confirmed at a blinded data review meeting to be held before the study database is locked for Part 1.

Part 2:

- **Part 2 Safety Set (P2SS):** The Part 2 Safety Set includes all participants who receive at least one dose of lixivaptan in Part 2.
- **Part 2 Efficacy Analysis Set (P2EAS):** The Part 2 Efficacy Analysis Set includes all participants in the Part 2 Safety Set who have at least one assessment of off-treatment eGFR in Part 2.

Parts 1 & 2 (Combined):

• Lixivaptan Treated Safety Set (LTSS): The Lixivaptan Treated Safety Set is defined as all participants who received at least one dose of lixivaptan treatment after randomization during the entire study. This analysis population will be used to summarize safety data during the study for all randomized, lixivaptan-treated participants.

6. General Issues for Statistical Analysis

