7.1. Disposition of Participants and Withdrawals

Disposition of participants in Part 1 will include, but not limited to, the following:

- The number of participants who
 - o Screened
 - Failed screening
 - Reasons failed screening
 - Placebo Run-in/Placebo Run-in Safety Set
 - Not completed
 - Reasons not completed
 - o Lixivaptan Titration/Lixivaptan Titration Safety Set
 - Not completed
 - Reasons not completed
- The number and percentage (percentage is calculated based on all the randomized participants) of participants who
 - Randomized/ITT
 - Treated/mITT/Randomized Safety Set
 - Completers/PEAS
 - On-treatment completers

- Off-treatment completers
- At least one on-treatment eGFR assessment/SEAS
- Discontinued from study drug early and reasons
- Not completed in Part 1 and reasons
- In PPAS

Disposition of participants in Part 2 will include, but not limited to, the following:

- The number and percentage (percentage is calculated based on all the continuing participants in Part 2) of participants who
 - Continued in Part 2
 - Treated/P2SS
 - At least 1 off-treatment eGFR/P2EAS
 - Discontinued from study drug early and reasons
 - Not completed in Part 2 and reasons

Note that Lixivaptan Treated Safety Set for Parts 1 and 2 combined consists of the participants who are randomized and treated (Randomized Safety Set) in lixivaptan treatment group in Part 1 and the participants who are treated (P2SS) in Part 1/Part 2 - Placebo/Lixivaptan cohort in Part 2.

7.2. **Protocol Deviations**

Protocol deviations will be tracked, recorded, and reviewed prior to database lock, following the Protocol Deviation Guidance Plan for this study.

Protocol deviations will be classified as "Important" or "Not Important".

Important protocol deviations include:

- Enrollment of a participant that did not meet inclusion criteria of the study/Enrollment of a participant that met exclusion criteria of the study.
- Missed safety assessments during Screening that are required for the thorough vetting of study inclusion/exclusion criteria are considered important deviations. They will be documented through failure of the respective Inclusion or Exclusion Criterion.
- Informed Consent Form (ICF) not obtained, or obtained after initiation of respective study procedures, important deviation from GCP consenting procedure, such as wrong version used, missing signature(s) and/ or date(s), ICF signed prior to IRB/IEC approval, other important deviation from GCP consenting process

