7.3. Demographics and Other Baseline Characteristics

Summary statistics for age, sex, race, ethnicity, height, weight, and BMI will be presented by treatment group.

For the continuous variables, the number of non-missing values and the mean, standard deviation, median, minimum, and maximum will be tabulated.

For the categorical variables, the counts and proportions of each value will be tabulated.

These analyses will be conducted for the Randomized Safety Set and PEAS (Part 1) and P2SS and P2EAS (Part 2).

The number and percent of participants with a family history of ADPKD, the counts and percentages of each method used to diagnose ADPKD, the counts and percentages of each Mayo Clinic ADPKD Classification, the counts and percentages of each CKD stage, and the time since diagnosis will be presented by treatment group for Part 1. The number and percent of participants prior treated with tolvaptan and associated safety information will be summarized by treatment group for Part 1. The number and percent of participants reporting various medical histories, grouped by MedDRA system organ class and preferred term (coded using MedDRA v.24), will be tabulated by treatment group. This analysis will be conducted for the Randomized Safety Set and PEAS (Part 1) and P2SS and P2EAS (Part 2).

In addition, the above summary will be presented for all the participants who entered in the Lixivaptan Titration Period (Lixivaptan Treated Safety Set).

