8.1. Definition of Completer and Non-completer

Part 1 completer and non-completer will be defined as the following:

- On-treatment completer: all the randomized participants who take double-blind study drug in accordance with the protocol through Visit 22 (Week 52), and complete some or all of their required trial visits/assessments through Visit 22 and have at least one follow-up serum creatinine assessment during off-treatment Follow-up Period I.
- Off-treatment completer: all the randomized participants who permanently discontinue double-blind study drug (or never begin double-blind treatment) and complete some or all of their required study visits/assessments through Visit 22 and have at least one follow-up serum creatinine assessment during Follow-up Period I.
- Non-completer: all the randomized participants who take the study drug (or never take the study drug) but do not complete the Visit 22/ET visit or complete Visit 22/ET visit and do not have at least 1 follow up serum creatinine assessment during Follow-up Period I.

Part 2 completer and non-completer will be defined as the following:

- On-treatment completer: all the randomized participants who enter Part 2 of the study, take open-label study drug in accordance with the protocol through Visit 42 (Week 104), and complete some or all of their required study visits/assessments through Visit 42 and have at least one follow-up serum creatinine assessment during Follow-up Period II.
- Off-treatment completer: all the randomized participants who enter Part 2 of the study, but permanently discontinue open-label study drug (or never begin open-label treatment) and complete some or all of their required study visits/assessments through Visit 42 and have at least one follow-up serum creatinine assessment during Follow-up Period II.
- Non-completer: all the randomized participants who enter Part 2 of the study, take the study drug (or never take the study drug) but do not complete the Visit 42/ET visit or

complete Visit 42/ET visit but do not have at least 1 follow up serum creatinine assessment during Follow-up Period II.

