8.5. Health Outcomes Analyses (Part 1)

The endpoints from ADPKD-Impact Scale (ADPKD-IS), ADPKD-Pain and Impact Scale (ADPKD-PDS), ADPKD-Urinary Impact Scale (ADPKD-UIS) Patient Reported Outcomes (PROs) will be evaluated separately by domain (see Section 4.1.2.2) for the PEAS. Missing data are not imputed prior to the analysis.

An analysis utilizing a MMRM will be performed on the changes in each domain score from baseline (visit 2) to all Double-Blind, Randomized Treatment Period visits up to Follow up Period I (i.e., Visits 12, 15, 18, 22 and 25). The MMRM will include treatment group, visit, treatment group-by-visit, and randomization stratification factors (CKD stage [CKD2 versus CKD3/4] and Mayo Clinic ADPKD Image Classification [1C, 1D, or 1E]) as fixed effects, baseline as a covariate, and the baseline-by-visit interaction. An unstructured variance-covariance matrix is assumed for the repeated measures. The treatment difference in change from baseline at each post-baseline visit will be produced from the analysis.

Example SAS code is shown below:

```
PROC MIXED EMPIRICAL ALPHA=0.01;

CLASS TREATMENT VISIT CKD_STAGE MAYO_CLASS USUBJID;

MODEL CHANGE = TREATMENT BASELINE VISIT VISIT*TREATMENT BASELINE*VISIT CKD_STAGE

MAYO_CLASS /SOLUTION CL;

REPEATED VISIT/TYPE=UN SUB= USUBJID;

LSMEANS VISIT*TREATMENT/ALPHA=0.01 PDIFF CL;

ESTIMATE 'Lixivaptan – Placebo Change from Baseline at Visit 12'

TREATMENT -1 1 VISIT*TREATMENT -1 0 0 0 0 1 0 0 0 0;
```

ESTIMATE 'Lixivaptan – Placebo Change from Baseline at Visit 15' TREATMENT -1 1 VISIT*TREATMENT 0 -1 0 0 0 0 1 0 0 0;

RUN;

...

In addition, descriptive summary (n, mean, standard deviation, median, minimum, and maximum) will be used to summarize the change from baseline in each domain score at the Lixivaptan Titration Period visits (Visits 4-9) for all the participants in the Lixivaptan Treated Safety Set.

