8.12. Additional Analyses (Part 2)

Additional exploratory analyses may be conducted to address any issues caused by potentially different treatment/exposure patterns between Part 1 and Part 2 for the participants in the P2EAS.

9. Safety and Tolerability Analysis

Safety will be evaluated from reported AEs, changes in clinical laboratory values, changes in

vital signs, and electrocardiogram (ECG results).

A Safety Analyses will be performed for the following:

- Single-Blind Placebo Run-in Period for the Placebo Run-in Safety Set (Part 1)
- Lixivaptan Titration Period for the Lixivaptan Treated Safety Set (Part 1)
- Double-blind, Randomized Treatment and Follow-up I Periods for the Randomized Safety Set (Part 1)
- Maintenance Treatment and Follow-up II Periods for the P2SS (Part 2)
- Double-blind, Randomized Treatment and Follow-up I Periods and Maintenance Treatment and Follow-up II Periods for the LTSS (Part 1 and Part 2 combined)

The tolerability will be summarized by:

- Incidence of participants with the maximum dose level taken by the final tolerated dose level determined for the double-blind treatment period during Lixivaptan Titration Period
- Count and percentage of participants up-titrated, down-titrated, remaining unchanged, or discontinued by the dose levels by visit (or time after titration initiation) during Lixivaptan Titration Period
- Count and percentage of participants by dose level by Visit (or time after randomization) during the double-blind treatment period in Part 1 by treatment group
- Count and percentage of participants by dose level by Visit (or time after initiation of maintenance period) during the maintenance period in Part 2 by treatment group

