9.6. Lixivaptan Treatment Safety Analysis

The lixivaptan treatment safety will summarize the following safety information occurred post the first dose of lixivaptan treatment after randomization during the study based on the LTSS by treatment cohort and overall:

- Incidence of special liver events (ALT > 3 x, AST > 3 x, ALT or AST > 3 x, and Total Bilirubin > 2 x ULN)
- Kaplan-Meier product-limit curve for special liver events
- Summaries of TEAEs (see Section 9.2)

- Overall summary of TEAEs
- o TEAEs by preferred term and causality
- TEAEs by preferred term and severity
- Treatment-related TEAEs by preferred term and severity

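### Titration-period safety and PRO summaries are assigned to an analysis set that requires a lixivaptan dose after randomisation

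*SAP*

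**What the plan says.** SAP Section 5 defines two sets whose names differ by one word.

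- The Lixivaptan Titration Safety Set takes anyone with at least one lixivaptan dose in the titration period of Part 1. Randomisation is not required.
- The Lixivaptan Treated Safety Set (LTSS), placed under Parts 1 and 2 combined, is "all participants who received at least one dose of lixivaptan treatment after randomization during the entire study". The list of abbreviations ties LTSS to this name, so the acronym and the full name are one set.

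Two later sections keep the post-randomisation meaning. Section 7.1 describes the LTSS as "the participants who are randomized and treated (Randomized Safety Set) in lixivaptan treatment group in Part 1" plus placebo-arm participants dosed in Part 2. Section 9.6 covers safety events occurring "post the first dose of lixivaptan treatment after randomization during the study based on the LTSS".

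Three sections then use the name for the titration period:

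- Section 9, second bullet: "Lixivaptan Titration Period for the Lixivaptan Treated Safety Set (Part 1".
- Section 8.5, descriptive PRO summaries: "Lixivaptan Titration Period visits (Visits 4-9) for all the participants in the Lixivaptan Treated Safety Set".
- Section 7.3, baseline summaries: "all the participants who entered in the Lixivaptan Titration Period (Lixivaptan Treated Safety Set".

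The only summary that uses the titration set is disposition in Section 7.1, under "Lixivaptan Titration/Lixivaptan Titration Safety Set". Protocol Section 8.13 had put titration safety on the Treated Safety Set, which protocol Section 8.3 defines by any study-drug dose in Part 1.

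**The concern.** Titration is each participant's first lixivaptan exposure in this study, and its summaries should describe everyone exposed. Membership of the LTSS depends on what happens later. A participant permanently stopped during titration, whether for intolerance, an adverse event or liver tests, is not randomised and so cannot qualify. Restricting the titration tables to the LTSS therefore selects on the outcome of titration and removes the people in whom it failed.

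The tables most exposed are any Section 9.2 summaries of adverse events leading to study drug discontinuation that are run for titration. The ADPKD-UIS, given at every titration visit, would likewise be summarised only for participants who later took lixivaptan after randomisation. Disposition and safety tables for the same period would also have different denominators.

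**Working it through.** The plan states no sample size, power or alpha on this point. The check compares set definitions.

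**Who is omitted.** Titration Safety Set minus LTSS, from the Section 5 definitions:

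| Group dosed in titration | In Titration Safety Set | In LTSS | Source |
|---|---|---|---|
| Stopped before randomisation | Yes | No | Protocol 4.2.2 |
| Placebo arm, no lixivaptan in Part 2 | Yes | No | SAP 7.1 |
| Lixivaptan arm, no dose after randomisation | Yes | No | SAP 8.1 |
| Lixivaptan arm, dosed after randomisation | Yes | Yes | SAP 5 and 7.1 |
| Placebo arm, dosed in Part 2 | Yes | Yes | SAP 7.1 |

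Section 8.1 provides for the third group in its definition of off-treatment completers: "all the randomized participants who permanently discontinue double-blind study drug (or never begin double-blind treatment". Whether anyone falls in that group is not stated.

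**Permanently stopped before randomisation and in the LTSS.** This number is 0, because membership needs a dose after randomisation. Not every liver-test stop is permanent: protocol Section 7.3.7.1.2 allows titration to be re-initiated, and such a participant could still be randomised and enter the LTSS.

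**Section 7.3.** The description (everyone who entered titration) and the bracketed label (the LTSS) name different groups once the Section 5 definition is applied.

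**Was the restriction intended?** The protocol's Treated Safety Set is wider than the titration set, since it includes participants who took only run-in placebo, but it did not require randomisation. SAP Section 15 records both lixivaptan sets as added and gives no decision to limit titration summaries to participants dosed after randomisation.

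**Size on the planned numbers (illustration only).** SAP Section 3.7 plans 900 lixivaptan and 450 placebo participants, with about 90% continuing into Part 2 (0.90 × 1350 = 1215, as stated). Assume that all 900 take a post-randomisation dose and that 90% of the placebo arm is dosed in Part 2:

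- LTSS = 900 + 0.90 × 450 = 1305
- Entrants to titration = 1350 / (1 − f), where f is an assumed titration failure rate
- Omitted = entrants − 1305

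| Assumed f | Entrants | Omitted | Share of entrants |
|---|---|---|---|
| 0% | 1350 | 45 | 3.3% |
| 5% | 1421 | 116 | 8.2% |
| 10% | 1500 | 195 | 13.0% |
| 20% | 1687.5 | 382.5 | 22.7% |

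The documents give no value for f.

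**The study as it ended.** SAP Section 12 reports 5 randomised, all terminated in Part 1. The Part 2 route into the LTSS is therefore empty, and the set holds at most 5 people, all from the lixivaptan arm. The split by arm is not given.

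**The case against.** The strongest reply is that this is a one-word slip whose intent is clear. Section 7.3 spells out the group it means. The titration bullet in Section 9 is tagged Part 1 although the LTSS is filed under both parts combined. Section 7.1 pairs titration with the right set. That is the likely cause, and it makes the point an internal inconsistency more than a considered choice of population. It does not make the text correct: the wrong name appears in three sections, and a programmer who follows Section 5 gets the wrong denominator.

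Several narrower points stand:

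- Section 7.3 conflicts with itself only once Section 5 is read in.
- The effect on discontinuation tables is conditional. Sections 9.2 and 9.2.1 present results by treatment group, which Section 6.1.2 attaches to Part 1 summaries after randomisation, and Section 9 does not say which tables are run for titration.
- The table shells are a separate document and may name the right set. The blinded data review before the Part 1 lock is another chance to catch the error.
- The Section 9 tolerability counts of participants discontinued in titration are not tied to the LTSS.

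The effect is also limited elsewhere. The key ALT endpoint is confined to the double-blind period (Section 4.1.4.1). Data listings, disposition with reasons and, for liver events, review by the Hepatic Events Review Committee still show participants omitted from the tables. Section 12 allows only a limited set of tables, and the documents do not say whether a titration table is among them.

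**Conclusion.** The concern holds. As written, Sections 9 and 8.5 restrict titration-period summaries to participants who took lixivaptan after randomisation, and Section 7.3 labels all titration entrants with a set that cannot contain them all. This rests on the documents' own definitions and needs no outside assumption.

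The number omitted is unknown. The percentages above rest on assumed titration failure rates and on applying the overall 90% continuation to the placebo arm. What is certain is that nobody permanently stopped before randomisation is in the LTSS, and that in this study the LTSS has at most 5 members. The practical consequence is small, but the correction should be made for any titration table still produced.

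**What to change.** In the second bullet of SAP Section 9, in Section 7.3 and in Section 8.5, replace Lixivaptan Treated Safety Set with Lixivaptan Titration Safety Set. Keep the LTSS for Section 9.6 and for the combined Part 1 and Part 2 analysis in the fifth bullet of Section 9. Check that the table shells agree, and apply the change to any titration table produced under Section 12. The cost is one set name in three places, with no new data.

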7.3.7.1.2 Liver Test Abnormalities during the Placebo Run-in and/or Lixivaptan Titration Period

Serum aminotransferase or total bilirubin levels that are $\geq 1.2 \times \text{ULN}$ to $2 \times \text{ULN}$ during the Placebo Run-in and/or Lixivaptan Titration Period will require holding the dose constant and a discussion with the medical monitor. Levels exceeding $2 \times \text{ULN}$ during the Placebo Run-in and/or Lixivaptan Titration Period will require reducing the dose or discontinuation of study drug (randomization will not occur) depending on the extent of the elevation and in consultation with the medical monitor. Weekly monitoring of liver chemistry tests will be conducted until the values are below the ULN. In consultation with the medical monitor and sponsor, continuation of titration can resume if study drug was continued. If study drug had been stopped, titration can be re-initiated at Level 1 (50 mg BID) with weekly monitoring of liver chemistry tests if the participant agrees to the increased monitoring, is informed of the potential risks, and agrees to re-initiating study drug.

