8.3 Populations for Analysis

Part 1:

The following populations will be used for analyzing the data from Part 1:

Treated Safety Set: The Treated Safety Set consists of all participants who received at least 1 dose of study drug in Part 1.

Randomized Safety Set: The Randomized Safety Set consists of all participants in the Treated Safety Set who are randomized and receive at least 1 dose of randomized study drug.

Primary Efficacy Analysis Set (PEAS): The PEAS consists of all participants in the Randomized Safety Set who have both baseline and at least 1 valid assessment of eGFR in the Follow-up Period.

Secondary Efficacy Analysis Set (SEAS): The SEAS consists of all participants in the Randomized Safety Set who have both baseline and at least 1 on-treatment assessment of eGFR.

Part 2:

The following populations will be used for analyzing the data from Part 2:

Long-term Safety Set: The Long-term Safety Set consists of all participants in the Randomized Safety Set of Part 1 who receive at least 1 dose of lixivaptan during Part 2.

Long-term Full Analysis Set: The Long-term Full Analysis Set consists of all participants in the Long-term Safety Set who have at least 1 on-treatment measurement of eGFR in Part 2.

Long-term Efficacy Analysis Set: The Long-term Efficacy Analysis Set consists of all participants in the Long-term Full Analysis Set who were randomized to lixivaptan in Part 1.

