8.13 Safety Analyses

All Safety Analyses will be performed separately for Parts 1 and 2 for the following:

- Single-Blind Placebo Run-in Period for the Treated Safety Set (Part 1)
- Lixivaptan Titration Period for the Treated Safety Set (Part 1) and Lixivaptan Retitration Period for the Long-term Safety Set (Part 2)
- The Double-blind, Randomized Treatment and Follow-up I Periods for the Randomized Safety Set (Part 1) and the Maintenance Treatment and Follow-up II Periods for the Long-term Safety Set (Part 2)

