4.2.3.1. Exploratory Endpoints

- The annualized percent change in htLV determined by MRI from baseline (posttreatment follow-up visit [Visit 25] after Week 52 in Part 1) to post-treatment follow-up during Follow-up Period II after Week 104 for on-treatment completers, or, for participants who discontinue study drug treatment prior to Week 104 [Visit 42], during the Follow-up Period 28 days following study drug treatment discontinuation in Part 2;
- Mean change from baseline in morning spot urine osmolality in Part 2; Baseline is defined as urine osmolality obtained at 28 days post-treatment follow-up visit (Visit 25) after Week 52 in Part 1.
- The annualized change in eGFR calculated from the 2021 CKD-EPIcr-cys_R equation from baseline to the post-treatment follow-up. The definitions of baseline eGFR, post-treatment follow-up eGFR and annualization are the same as the key comparison endpoint in Part 2 (Section 4.2.1.1) except for using the different eGFR equations.

5. Analysis Populations

The following analysis populations are planned for this study:

Part 1:

- **Placebo Run-in Safety Set:** The Placebo Run-in Safety Set includes all participants who received at least one dose of placebo during Placebo Run-In Period in Part 1.
- Lixivaptan Titration Safety Set: The Lixivaptan Titration Safety Set includes all participants who received at least one dose of lixivaptan during Lixivaptan Titration Period in Part 1.
- **Randomized Safety Set:** The Randomized Safety Set includes all participants who received at least one dose of study drug after randomization.
- Intent-to-Treat Analysis Set (ITT): The ITT includes all participants who were randomized in Part 1.

- **Modified Intent-to-Treat Analysis Set (mITT):** The mITT includes all participants in the ITT who received at least one dose of study drug in Part 1. Note that the mITT Analysis Set consists of the same set of the participants in the Randomized Safety Set.
- **Primary Efficacy Analysis Set (PEAS):** The PEAS includes all participants in the mITT Analysis Set who have both baseline and at least one assessment of eGFR after the treatment is complete or discontinued in Part 1.
- Secondary Efficacy Analysis Set (SEAS): The SEAS includes all participants in the mITT Analysis Set who have both baseline and at least one on-treatment assessment of eGFR.

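### SAP Section 9 names the wrong set for titration-period safety: taken literally, the titration tables omit everyone who stopped during titration

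*SAP*

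**What the plan says.** SAP Section 9 lists the periods for which safety will be analysed and gives each one a set. The titration entry reads "Lixivaptan Titration Period for the Lixivaptan Treated Safety Set (Part 1").

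SAP Section 5 says the Lixivaptan Treated Safety Set is "defined as all participants who received at least one dose of lixivaptan treatment after randomization during the entire study". SAP 7.1 spells out its members, beginning "Note that Lixivaptan Treated Safety Set for Parts 1 and 2 combined consists of the participants who are randomized and treated" in the lixivaptan arm of Part 1 and adding placebo-arm participants who are treated in Part 2.

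SAP Section 5 also defines a Lixivaptan Titration Safety Set, which "includes all participants who received at least one dose of lixivaptan during Lixivaptan Titration Period". SAP 7.1 uses it for disposition, but the Section 9 list does not use it.

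Protocol 8.13 makes a different assignment: "Lixivaptan Titration Period for the Treated Safety Set (Part 1"). Protocol 8.3 explains that set: "The Treated Safety Set consists of all participants who received at least 1 dose of study drug in Part 1".

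**The concern.** Titration is the first lixivaptan exposure in the study, and liver chemistry is its key safety concern. Under Protocol 7.3.7.1.2, aminotransferase or bilirubin values above 2 x ULN during run-in or titration "will require reducing the dose or discontinuation of study drug (randomization will not occur) depending on the extent of the elevation". Titration can be restarted in some of these participants. Those who are not restarted, and those who stop for poor tolerability, leave the study without being randomized.

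A titration table built on a set defined by dosing after randomization contains none of them. The SAP 9.2 row for adverse events leading to permanent discontinuation would then count nobody who stopped permanently in titration. Liver elevations that prevented randomization would also be missing from the titration summaries. The table would describe only people who had already shown that they could tolerate the drug.

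**Working it through.** No sample size, power or alpha figure is involved. The check is one of set membership, using the definitions in SAP Sections 5 and 7.1, Protocol 8.3, and Protocol 4.2.2, under which titration failures stop before randomization.

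| Participant | Protocol Treated Safety Set | Lixivaptan Titration Safety Set | Lixivaptan Treated Safety Set |
|---|---|---|---|
| Took run-in placebo only | in | out | out |
| Took lixivaptan in titration, stopped there | in | in | **out** |
| Randomized to lixivaptan and dosed | in | in | in |
| Randomized to placebo, takes lixivaptan in Part 2 | in | in | in |
| Randomized to placebo, never takes lixivaptan in Part 2 | in | in | **out** |

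The second and fifth rows are the gap. Both groups took lixivaptan during titration, and both fall outside the set named in Section 9. For titration failures the number included is 0 by definition, with no assumption needed.

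The placebo row can be sized from the planned numbers (Protocol 8.1, SAP 3.7):

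- Randomized: 900 lixivaptan + 450 placebo = 1350. All of them took lixivaptan in titration.
- Expected to continue into Part 2: 0.90 x 1350 = 1215, so 1350 - 1215 = 135 do not continue.
- Assuming equal continuation in both arms and that all 900 in the lixivaptan arm are dosed, the named set holds 900 + 0.90 x 450 = 900 + 405 = 1305.
- Randomized participants left out: 1350 - 1305 = 45.
- Limits if continuation differs by arm: 0 if all 135 non-continuers are on lixivaptan, 135 if all are on placebo.

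The number of titration failures cannot be sized in this way, because the documents state no titration drop-out rate.

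For the study as it ended, SAP Section 12 reports 5 randomized, all terminated in Part 1. Nobody could enter the set through Part 2 dosing, so it holds at most 5 people. Anyone else who took lixivaptan in titration is outside it.

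Nothing records this as a decision. SAP Section 15 lists the Titration and Treated sets as separate additions to the protocol's sets and gives no reason to take titration failures out of titration safety.

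**The case against.** The best counter-argument is that the SAP shows whom it means. SAP 7.3 uses the same name for everyone who entered titration. The Section 9 titration bullet carries a Part 1 tag, whereas the last bullet in the list uses the abbreviation LTSS for Parts 1 and 2 combined, which is the post-randomization sense. The literal reading also fits a Part 1 table poorly: a placebo participant's membership would depend on Part 2 dosing, yet Part 1 is to be analysed once Part 1 is complete (SAP Section 11). This stands as evidence that the name is a slip. It does not make the text correct, because one name now carries two memberships and the formal definition in Section 5 is the one a programmer would apply.

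It is also true that titration stoppers stay visible elsewhere. SAP 7.1 tabulates titration non-completion and its reasons on the correct set. SAP 6.1.7 puts all collected data in listings. SAP 9.2 to 9.2.2 require listings of all adverse events, events leading to discontinuation, deaths and serious events. SAP 11.2 brings the hepatic committee's adjudications into safety reporting. All of this stands and limits the harm to the summary tables.

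A reader might infer that the tolerability summary loses its stoppers too. The documents do not support that. Those bullets name no set, and one of them asks for "Count and percentage of participants up-titrated, down-titrated, remaining unchanged, or discontinued by the dose levels by visit" during titration, which makes sense only if stoppers are included. This is further evidence that inclusion was intended.

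**Conclusion.** Wrong as written; minor. The titration bullet in SAP Section 9 names a set that by definition contains no titration failures and omits placebo participants never dosed with lixivaptan in Part 2. That conflicts with Protocol 8.13 and with the SAP's own use of the name in 7.3. The most likely explanation is a wrong set name.

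A reader might infer that the SAP deliberately removes early liver or tolerability failures from safety reporting, or that the key liver result is biased. Neither is supported. No such choice is recorded, the disposition table and listings keep these people, and the key ALT endpoint in SAP 4.1.4.1 is confined to the double-blind period.

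The effect is therefore on the titration-period summary tables and on the patient-reported outcome summaries at titration visits in SAP 8.5, which use the same name. The figure of 45 placebo participants rests on the planned numbers and equal continuation by arm. The number of titration failures is unknown. With 5 randomized and only limited tables planned, the practical consequence is small.

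**What to change.** In the titration bullet of SAP Section 9, and in the last paragraph of SAP 8.5, replace Lixivaptan Treated Safety Set with Lixivaptan Titration Safety Set. In SAP 7.3, change the label in parentheses to match; the population described there in words is already right, so no output changes. Keep the Lixivaptan Treated Safety Set for the combined Part 1 and Part 2 analysis.

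The Titration Safety Set is a better denominator than the protocol's Treated Safety Set for this period, because it leaves out people who took only run-in placebo. One line in SAP Section 15 can record that departure.

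The cost is a name change in three places and one line of explanation. No new data, analysis set or analysis is needed.
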